Clinical Investigation Plan (Klinischer Prüfplan), Version 1.2

Central programming in patients with a bionic hand after traumatic brachial plexus injury

„Zentrale Programmierung von PatientInnen mit einer bionischen Rekonstruktion nach einer Plexusparese“

Sponsor

Medizinische Universität Wien, Universitätsklinik für Chirurgie
[name]
[name]

Principal Investigator („Prüfarzt“):

Univ.-[name]. [name]
Medizinische Universität Wien, Universitätsklinik für Chirurgie
Klinisches Labor für bionische Extremitätenrekonstruktion
[name]
[name]

Lead Investigator:

Dr. ir. [name]
Haaglanden Medical Centre
The Hague, The Netherlands
(Visiting Researcher at Medical University of Vienna, Austria)

CIP authors:

[name]
[name]
[name]
[name]
[name]
[name]
[name]

Index

Abstract	3
Introduction	4
Research questions	5
Hypothesis	5
Design	5
Risk-benefit assessment	9
Experimental subjects: informed consent procedure	9
Discontinuation/withdrawal of participants from study	10
Duration and scale	10
Procedure for handling study results	10
Compensation	11
Safety reporting and insurance	11
Agreements on publication	11
Funding statement	11
References	11

Abstract

Traumatic brachial plexus lesions may lead to permanent impairment of hand function despite brachial plexus surgery. In selected cases the affected forearm can be amputated and replaced by a bionic hand. It is unclear how cortical activation patterns change after the injury and after acquisition of the hand prosthesis considering the complex changes in sensory and motor feedback.

The aim of the study is to measure cortical activity with fMRI during actual and imagery movements with the affected and healthy arm in a group of patients after traumatic brachial plexus injury and a group in whom this was followed by replacement with a bionic hand.

In this prospective study three groups of patients will participate: 1) 3 adult patients with a traumatic brachial plexus lesion eligible for a bionic arm but prior to its acquisition, 2) 3 patients with a traumatic brachial plexus lesion who have acquired the bionic arm already, and 3) 10 healthy subjects. We will measure cortical activity using fMRI BOLD tasks of closing the hand and motor imagery of this movement. Cortical activity will be compared between the three groups. Additionally, regional gray matter volume, resting-state, and DTI networks will be studied. Written informed consent will be provided prior to the investigation. The complete examination has a duration of approximately 45 minutes.

Introduction

In this study we want to investigate what changes take place in the brain after a traumatic brachial plexus lesion followed by acquiring a bionic hand. These patients have acquired a global brachial plexus injury including avulsions of the lower nerve roots (C8-Th1), which are responsible for hand function. They have a poor hand function despite brachial plexus surgery. After an extensive training program these patients acquire a myoelectric hand prosthesis (Sensor hand speed (Otto Bock HealthCare Deutschland, GmbH, Germany) or similar) and their affected hand is amputated. The acquired bionic hand is surface EMG driven by the remaining arm muscles after nerve and muscle transfer, if necessary. (Aszmann, et al., 2015; Sturma et al, 2018) Thus, the patients have to learn how to control the bionic hand with new motor and sensory feedback signals. It is unclear what changes occur in the brain to succeed at this.

Functional MRI (fMRI) can identify cortical plasticity in humans. (Anastakis et al., 2005) Additional motor imagery tasks allow us to assess the changes in cortical areas involved in motor planning. (Decety and Grezes, 1999) We know that motor cortical areas expand at the onset of learning a new motor skill in healthy subjects, but also in patients following upper extremity injury and reconstruction. (Anastakis et al., 2005) These areas decrease again when a skill is being mastered. (Anastakis et al., 2005) In amputees a higher contralateral cortical activation was found during imagined phantom hand movements compared to healthy subjects. (Lotze et al., 2001) It has been suggested that this is due to an increased central effort required for action planning. (Hotz-Boendermaker et al., 2008) However, motor imagery ability of the affected and unaffected limbs in patients with complete traumatic brachial plexus palsy has been shown to decrease, possibly due to long-term disuse. (Date et al., 2019) And in adults with an obstetric brachial plexus lesion cortical activation is increased only for movement planning but not actual movement. (Anguelova et al., 2017) Cortical changes have also been found when using the healthy arm in these patients. (Anguelova et al., 2017)

Thus, the aim of this study is to elucidate with fMRI what changes occur in cortical activity in patients with a traumatic brachial plexus lesion followed by forearm amputation and acquisition of a bionic hand. Understanding what cortical changes occur, may help us in the future to acquire a better patient selection for this intervention and possibly improve rehabilitation schemes.

Research questions

- 1) Does the cortical activation increase in the contralateral hemisphere during movement of the corresponding affected arm after traumatic plexus lesion compared to healthy subjects?
- 2) Are different cortical areas activated in the contralateral hemisphere during movement of the affected arm after traumatic plexus lesion than those in healthy subjects or does the expected area of activation expand?
- 3) Does cortical activity increase or expand in the ipsilateral hemisphere (responsible for the healthy arm) during movement of the affected arm after traumatic plexus lesion?
- 4) Does cortical activity increase or expand in both hemispheres during movement of the healthy arm after traumatic plexus lesion?

All of the above questions will be addressed for two groups of patients: 1. patients who are eligible for bionic reconstruction but have not acquired it yet, and 2. patients with a bionic arm.

Hypothesis

Cortical activity increases and the area expands which is responsible for performing and planning a motor task in patients after traumatic brachial plexus lesion prior as well after bionic hand acquisition compared to healthy control subjects for both the affected and unaffected side.

Design

a) Selection of experimental subjects

A group of 3 adult patients who acquired a bionic hand at the Medical University of Vienna after a traumatic brachial plexus lesion, and a group of 3 patients eligible for the bionic hand prior to a possible amputation will be included. The number of patients included is based on the rarity of the procedure and thus the very limited number of eligible study participants. Ten control subjects will be included for comparison. An inclusion criterion for all participants is an age above 18, and that they understand German or English. Brachial plexus surgery is not an exclusion criterium for patients. Patients with a bionic hand are selected who are able to open and close the hand prosthesis. The standard contraindications for MRI will be checked for according to hospital protocol (ferromagnetic devices such as clips, claustrophobia, etc.) and, if necessary, patients will be excluded from participation.

b) Procedure

Cortical activation is measured with a Philips Achieva 3 Tesla MRI scanner at the University Department of Radiology and Nuclear Medicine of Vienna General Hospital. The MRI protocol will include the following sequences: T1-weighted anatomical scan, T2-weighted task related scans, resting-state, and DTI-sequence.

Participants are requested to isometrically close their hand at the rate of 1Hz. This means to repeatedly squeeze their closed fist tight without an observed movement, thus avoiding MRI movement artifacts. This movement is selected based on a surface EMG signal to noise ratio higher than 3 in the patients with a bionic hand from a pilot study prior to this investigation. The arms are positioned in a straight position next to the body with the hand palm facing the body. Participants are instructed to lie still during the experiment. For the motor imagery task, participants are requested to imagine rhythmically (1Hz) performing the same movement. The tasks (execution and imagery) are performed by all participants (all three groups) with both arms separately.

Task based fMRI will be applied using a block-design-paradigm to assess cortical activation patterns. Task instructions are represented by a visual and an audio cue. The visual cue is an image of a hand, either left or right corresponding to the task, which is presented on a computer screen using SensaVue and projected onto a mirror above the eyes of the subject. The audio cue indicates to either execute or imagine isometrically closing the hand and states which side to use (left or right). The audio instructions are given by the investigator through the MRI intercom before the start of the task. A crossed hand indicates rest (baseline). A thirty second baseline block is presented followed by a thirty second task block, comprising one cycle. A cycle is repeated five times during a total of five minutes. A total of four conditions is used in the same order for all participants: 1. execution left arm, 2. execution right arm, 3. imagery left arm, 4. imagery right arm. Subjects are given a break to rest (not scanning) between the four conditions, until they indicate they are ready to continue, to minimize the effects of (muscle) fatigue.

A 10 minute fMRI resting-state sequence will be acquired to assess ongoing functional communication between brain regions during rest. For this sequence participants are instructed to think of nothing in specific while keeping the eyes closed. An 8 minute DTI-sequence will be acquired to assess the structural/anatomical brain connectivity; thus, no specific task is requested from participants.

An electromyography (EMG) training session prior to MRI scanning is used to assure the tasks are executed as requested. EMG is measured with electrodes placed over the muscle belly of the flexor digitorum superficialis and profundus in control subjects, the healthy arm in all patients, and the affected arm in patients who have not undergone amputation and prosthetic fitting yet. (Hermens et al., 1999) For the patients who have acquired a bionic hand already, the position of the electrode used for “hand close” within their prosthetic fitting is used. During MRI measurement the bionic hand is placed outside the MRI scanner as it is not MRI compatible but could be observed by the patients during the EMG training session. During the training session participants observe their EMG activity during the tasks on a screen. They are instructed to aim for activity in the agonist and reduce activity in the antagonist as much as possible during execution and not to activate both agonist and antagonist during imagery squeezing of the fist. Responses are acquired using a band pass filter of 20 Hz–2 kHz and recorded over a minimum of 100 s using. For recording the surface EMG either the MyoBoy in combination with the PAULA Software (both from Ottobock Health Care GmbH, Duderstatt, Germany) or the TeleMyo 2400T G2 System with myoMUSCLE Master software (both from Noraxon, Scottsdale, US) will be used. Both systems are CE-certified medical products.

b) Analysis

Cortical activity is compared between patients and control subjects as follows.

fMRI data will be preprocessed with the SPM12 software package (Wellcome Department of Cognitive Neurology, Institute of Neurology, University College London, UK) in the MATLAB R2017a programming environment (MathWorks, Inc.; Natick, MA, USA). The following processing steps are applied: motion correction (Jenkinson et al., 2002), removal of non-brain tissue, (Smith, 2002) spatial smoothing using a Gaussian kernel of 8 mm full width at half maximum, grand-mean intensity normalization of the entire 4D dataset by a single multiplicative factor and high-pass temporal filtering (Gaussian-weighted least-squares straight line fitting, with a 128 s cut-off). To register fMRI scans to standard space, functional scans of an individual are registered to the corresponding T2-weighted images, which are registered to the T1-weighted images, followed by registration to MNI-152 standard space (T1 standard brain averaged over 152 subjects; Montreal Neurological Institute, Montreal, QC, Canada) images (Jenkinson and Smith, 2001; Jenkinson et al., 2002). Preprocessed MRI data of patients with an affected left arm are mirrored with respect to the midsagittal plane (Ward and Frackowiak, 2003). In this way the hemisphere corresponding with the affected hand is on the same (left) side for all patients and the right hemisphere corresponds with the unaffected hand. This is also done for the healthy subjects: the hemisphere responsible

for the non-dominant hand will, if necessary, be mirrored to be on the left side. Patients will be asked for how many days of the week and how many hours a day on average they have used the prosthesis in the past two weeks, as a possible correction factor (independent variable) for the amount of motor cortex activation. Additionally, resting-state networks, DTI data and regional gray matter volume will be compared between patients and healthy subjects.

EMG activity before MRI scanning is compared for the patient and control groups, and for each muscle and task separately. To exclude learning effects the first 50 s of the EMG signal for each of the four conditions (motor imagery/movement, right/left hand) are excluded from analysis. The EMG signal is then rectified and the sum of values between 50 and 100 s of the recording is calculated. The non-parametric dependent samples Wilcoxon's test is used in IBM SPSS Statistics 25 with a significance threshold of 0.05.

Risk – benefit assessment

The risk for study participation is negligible. If the experienced inconvenience turns out to be unexpectedly greater than estimated by the subject beforehand then participation in the investigation is stopped immediately.

As no medical treatment is delivered, the benefits for the participants will be relatively little. For some of the amputees or participants with severe nerve injuries, it might be interesting to better understand how they cortically adapted to the situation. Additionally, participants will support basic research that might in the future have applications in the field of human-machine interfacing in healthy people and individuals with injuries and impairments. It is, however, unlikely that the cohort of participants supporting us within this study will ever directly benefit from the experiments.

In summary, we do neither expect any great benefits nor any risks for the participants. As this is basic research, we do, however, hope to be able to use the findings to develop better rehabilitation technology in the future. This might include better interfaces for prosthetic control as well as better tools for the rehabilitation after nerve injuries.

As we cannot guarantee that the participants will benefit from any of the possible future applications, we plan to compensate their time spend within the study with 10€/hour and reimburse their travel expenses.

Experimental subjects: informed consent procedure

Written informed consent will be required before performing the investigation. Not participating in the study or withdrawal from the study will not have any negative effects for the participants and will not affect the medical treatment of patients.

Discontinuation/withdrawal of participants from study

Each participant has the right to withdraw study at any time without needing to give a reason for withdrawal. In addition, the investigator may discontinue a participant from the study at any time if the investigator considers it necessary for any reason including:

- Ineligibility
- Significant protocol deviation
- Significant non-compliance with study requirements
- An adverse event which makes further participation not possible
- Consent withdrawn

The reason for withdrawal will be recorded. If the participant is withdrawn due to an adverse event, the investigator will arrange for follow-up visits or telephone calls until the adverse event has resolved or stabilised. Only after participant approval, data already collected before withdrawal from the study will be included in the analysis.

Duration and scale

Participants will be contacted and scanned (training session prior to scanning included) from September 2020 onwards (pending ethical approval).

Eligible participants will receive an information letter with an attached informed consent form and an enclosed return envelope.

Expected time for scanning is 45 minutes. Including the time for EMG training and instructions before scanning, the full duration of one experiment is 1.5 to 2 hours.

Procedure for handling study results

Research data will be processed under a number for each patient. The gathered MRI scans will be saved and managed corresponding to that number in a file. The data are accessible exclusively to the involved investigators:

- Dr. ir. [name], Haaglanden Medical Centre, The Hague, The Netherlands
- [name], Medical University of Vienna
- [name], Medical University of Vienna
- [name], Medical University of Vienna
- [name], Medical University of Vienna
- [name], Medical University of Vienna
- [name]. [name], Medical University of Vienna

We will not share any study results with researchers outside the EU. Currently, there are no plans for making any data sets fully publicly available via any open data platform. If any data sets will be made publicly available in the future, this will happen after consultation of the Medical University of Vienna's data clearing committee. (<https://www.meduniwien.ac.at/web/ueber-uns/organisation/gremien/daten-clearingstelle/>).

Should incidental findings of clinical relevance occur, we will follow the recommendations from "Managing Incidental Findings in Human Subjects Research: Analysis and Recommendations" by Wolf S et al.

Compensation

Traveling expenses and time spent on the experiment will be compensated for with 10€/hours.

Safety reporting and insurance

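### The EMG task check has no rest recording and no preset criterion, so its raw sum cannot by itself show that imagery was silent

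*Combined protocol and SAP*

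**What the plan says.** **Purpose.** Under Design, b) Procedure, the EMG training session "is used to assure the tasks are executed as requested". Participants are told to work the agonist in execution and, in imagery, "not to activate both agonist and antagonist during imagery squeezing of the fist". Feedback is live: "During the training session participants observe their EMG activity during the tasks on a screen". No pass level is given.

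**Electrode site.** Finger-flexor electrodes are used in controls, "the healthy arm in all patients, and the affected arm in patients who have not undergone amputation and prosthetic fitting yet". The affected arm of the bionic group is recorded elsewhere: "For the patients who have acquired a bionic hand already, the position of the electrode used for" closing the prosthesis.

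**Equipment.** Either of two recording systems may be used.

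**Outcome.** Under Design, b) Analysis, the first 50 s of each of the four task recordings are dropped. Then: "The EMG signal is then rectified and the sum of values between 50 and 100 s of the recording is calculated". No rest recording, baseline correction or normalisation is described.

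**Comparison and test.** "EMG activity before MRI scanning is compared for the patient and control groups, and for each muscle and task separately". The test is introduced as "The non-parametric dependent samples" Wilcoxon test, at a threshold of 0.05. Whether it is one- or two-sided is not stated.

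**The concern.** The stated purpose needs an answer for each person, arm and task: was the muscle active in execution, and silent in imagery? The sum of a rectified signal has no value that means silent, because noise alone makes it positive. It becomes informative only against a reference, and none is planned.

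A comparison with controls does not supply that reference. According to the Introduction, all patients have lower-root avulsions and poor hand function, so signal amplitude may differ from controls at equal effort. In three arms the electrode also sits at a different place.

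The hypothesis separates performing a movement from planning it. No EMG is described during scanning, so this session is the only EMG evidence in the plan that imagery was not weak execution. If it cannot answer that, a reader of the imagery results is left with the instruction and the on-screen feedback alone.

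**Working it through.** The plan states no EMG amplitude, power or pass level, so there is no figure to reproduce. Inputs from the plan are the group sizes (3 bionic-hand, 3 before bionic reconstruction, 10 controls), the 50-100 s window and a visit of 1.5 to 2 hours. Everything marked as assumed is illustration.

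**1. What the raw sum can separate.** For a zero-mean Gaussian signal, the expected rectified sum is N × SD × √(2/π), where N = 50 s × sampling rate. Assume 1000 Hz (the rate cancels in the comparison), so N = 50,000.
- Silent, noise SD 1: 50,000 × 0.798 = 39,894.
- Active half the time with signal amplitude 3 over the same noise: 50,000 × 0.798 × (0.5 × √10 + 0.5) = 83,025.
- Ratio: 83,025 / 39,894 = 2.08.

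A silent recording with 2.08 times the noise or gain therefore gives the same sum as this active one. Divided by rest at the same electrode, the two separate: 1.0 for the silent recording, whatever its noise level, and 2.08 for the active one. If signal-to-noise is 3, the ratio runs from about 1.2 to 3.2, depending on how that figure is defined and on 25% to 100% active time.

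**2. Where site differs.** 16 participants × 2 arms = 32 arms. Three are recorded at the prosthesis hand-close position and 29 over the finger flexors. In the 3 patients before bionic reconstruction the site matches controls, so there only injury is mixed in.

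**3. Size and direction of the mixing.** These cannot be derived from the documents. Two assumed cases show this. Both use equal task performance, log-normal amplitudes with SD of log amplitude 0.3 to 0.7, and an exact independent-samples rank test of 6 v 10 (not named in the plan).
- Amplitude halved in all 6 patients: significant in 38% to 97% of simulated studies.
- Doubled in the 3 bionic arms and halved in the other 3: 0% to 1.4%.

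**4. The named test.** Patients and controls are different people, so there are no pairs for a dependent-samples test. Within a group, the smallest exact two-sided p is 2/2ⁿ:
- n = 3: 0.25
- n = 6: 0.031
- n = 10: 0.002

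**5. How an example rule behaves.** Take one-second windows and a threshold of rest mean + 3 SD, and call imagery silent if at most 5 of 50 windows exceed it. Assumed: window coefficient of variation 0.1 to 0.3.
- Drift SD between recordings up to 0.1 on the log scale: about 0% to 9% of truly silent arms are flagged (0 to 3 of 32).
- Drift SD 0.2: about 6% to 24% (2 to 8 of 32).

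The documents give no drift figure, so the cut-offs must come from pilot data.

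**The case against.** **The plan does have a check.** It has live feedback, an explicit instruction to stay silent in imagery, selection of bionic-hand patients who can open and close the prosthesis, and a pilot signal-to-noise ratio above 3 in bionic-hand patients. The discontinuation section also allows removal for significant non-compliance. This stands, so it would be wrong to infer that task performance goes unchecked. But none of these sets a level for these recordings, and only the feedback and the instruction bear on imagery.

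**The dependent-samples test may point to a within-person contrast.** Execution against imagery at the same electrode would fit the named test and largely cancel site, injury and gain. With assumed execution at 3 times the noise floor, silent imagery and within-person SD 0.2 to 0.5, it is significant in 73% to 100% of studies at n = 6 and 99% to 100% at n = 10. Existing recordings could thus support relative activation. But the text has each task compared separately, so this contrast is not clearly planned, and it would not show that imagery is silent.

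**The effect of injury and site is speculative.** This stands. A reader might infer that lower amplitude in injured arms will usually produce a false group difference. The second case in the working shows that this rests on assuming loss in every patient, which nothing in the documents establishes for the prosthesis-control site. A reader might also infer that two recording systems bias the result; that needs unbalanced use and different scales, and neither is shown.

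**EMG is peripheral.** Also fair. All research questions concern cortical activity, and the plan never says that a raw EMG difference will be read as task performance.

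**Conclusion.** The point holds as a minor improvement. Followed exactly, the plan cannot show from its EMG outcome that imagery was silent, because there is no rest reference and no criterion. This follows from the text and from the fact that a rectified sum is positive in silence; it does not depend on the simulations.

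A patient-control difference in the sum cannot be read as task performance. It also carries injury in all 6 patients and electrode site in 3 of 32 arms, with unknown size and direction. The mismatch of the test depends on reading the paragraph as a patient-control comparison, which is its natural sense. The p of 0.25 for n = 3 assumes a two-sided exact test.

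The documents do not support the further step that the fMRI findings are invalid. EMG enters no fMRI model, and a missing criterion is not evidence that tasks were done wrongly.

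**What to change.** 1. **Design, b) Procedure:** record about 50 s of rest EMG per arm at each electrode used, in the same session. Use one recording system for all recordings of a given participant; a single system for everyone is not needed.
2. **Design, b) Analysis:** replace the raw sum by the mean rectified amplitude over 50-100 s of the task divided by the mean at rest at the same electrode. Report it per person, arm and task.
3. **Criteria:** fix the active and silent criteria before the first participant, from pilot recordings that include drift between repeated rest recordings. Mark failing tasks in the fMRI results. The 3 SD and 5-of-50 values above are examples only.
4. **Tests:** use the dependent-samples Wilcoxon test only for within-person contrasts (task v rest, execution v imagery), and an independent-samples rank test for any patient-control comparison. Keep groups of 3 descriptive.
5. **Interpretation:** state that a raw patient-control difference is not read as task performance, nor a non-significant imagery test as silence.

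**Cost.** Wording in two sections, plus 2 × 50 = 100 s per participant beside the 4 × 100 s already recorded: 100/7200 = 1.4% to 100/5400 = 1.9% of the visit.

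**Downsides.** The ratio does not make different muscles equivalent or remove the effect of injury. Over an unchanged noise floor, halving a signal of 10 times the floor takes the ratio from √(1 + 10²) = 10.0 to √(1 + 5²) = 5.1. Not active therefore means no detectable activity, not lack of effort, and weak imagery activity can still be missed.

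### The only test named for the EMG comparison of patients and controls is a dependent-samples test, but the groups are different, unmatched people and no within-person contrast is defined

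*Combined protocol and SAP*

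**What the plan says.** The EMG paragraph of Design, b) Analysis states: "EMG activity before MRI scanning is compared for the patient and control groups, and for each muscle and task separately". The outcome is one number per recording, the sum of the rectified signal from 50 to 100 s. The test sentence is "The non-parametric dependent samples Wilcoxon's test is used in IBM SPSS Statistics 25", with a threshold of 0.05. Sidedness, and whether p is exact or asymptotic, are not given. No other test is named for EMG.

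Design, a) Selection of experimental subjects sets the groups: "A group of 3 adult patients who acquired a bionic hand at the Medical University of Vienna after a traumatic brachial plexus lesion"; "a group of 3 patients eligible for the bionic hand prior to a possible amputation will be included"; and "Ten control subjects will be included for comparison". It gives no matching or pairing rule.

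Design, b) Procedure gives the purpose of the measurement: "An electromyography (EMG) training session prior to MRI scanning is used to assure the tasks are executed as requested". It also says: "The tasks (execution and imagery) are performed by all participants (all three groups) with both arms separately". Electrodes sit over the finger flexors in controls, in the healthy arm of all patients and in the affected arm of patients not yet amputated. In patients who already have the bionic hand, the affected-arm electrode sits where the prosthesis takes its hand-close signal. Either of two recording systems may be used.

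**The concern.** A dependent-samples Wilcoxon (signed-rank) test works on differences within linked pairs. Patients and controls here are separate people in unequal numbers, and nothing links a given patient to a given control. As worded, the named test cannot make the named comparison.

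The sentence can also be read as a comparison of conditions within each person, done for each group. The test type is then sound, but the plan does not say which two conditions form the pair, and patients against controls are left with no test.

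At stake is what the EMG check can show. If patients and controls differed in muscle activity during execution or imagery, that would bear on how a difference in cortical activation is read. A test that cannot be significant in a group of 3 gives no information on this, and its non-significance could be mistaken for equal performance.

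**Working it through.** The plan gives no power, effect size or calculated sample size for EMG, so there is no figure of its own to reproduce. The check asks whether each reading of the test sentence can work at the planned group sizes.

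**Inputs.** Groups of 3, 3 and 10 (Design, a) Selection of experimental subjects); threshold 0.05 (Design, b) Analysis). Assumptions: two-sided testing, no ties.

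**Reading 1: patients against controls, signed-rank test.** Every observation needs a partner. With one patient group, 10 − 3 = 7 controls have none. With the patients pooled, 10 − 6 = 4 have none. The plan has no rule for forming pairs, so the test cannot be run as written.

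**Reading 2: within person, signed-rank test.** With n pairs there are 2^n equally likely sign patterns under the null, so the smallest exact two-sided p is 2/2^n:
- n = 3: 2/8 = 0.25 (one-sided 1/8 = 0.125)
- n = 6: 2/64 = 0.031
- n = 10: 2/1024 = 0.002

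For the normal approximation without continuity correction, the mean is n(n+1)/4 and the variance n(n+1)(2n+1)/24. At n = 3 the mean is 3 and the standard deviation is √(84/24) = √3.5 = 1.871. The largest z is therefore 3/1.871 = 1.604, which gives two-sided p = 0.109. A patient group of 3 cannot reach 0.05 by either method.

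**Alternative: patients against controls, independent-samples rank-sum test.** With groups of a and b, the smallest exact two-sided p is 2/C(a+b, a):
- 3 v 10: 2/286 = 0.0070
- 6 v 10: 2/8008 = 0.00025
- 3 v 3: 2/20 = 0.10

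Full enumeration gives an attained size at the 0.05 level of 0.0490 for 3 v 10 and 0.0420 for 6 v 10. This test uses all 10 controls, needs no pairs and keeps its level. It cannot separate the two patient groups from each other, because 3 v 3 stops at 0.10.

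These minimum p-values depend only on the group sizes, not on any assumed EMG values. They show whether significance is possible, not how likely it is.

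**The case against.** The strongest defence is that the authors meant a within-person test. The EMG sentence says *for* the groups, whereas the same section uses *between* for cortical activity, resting-state, DTI and gray matter. Everyone performs both tasks with both arms, the four conditions are listed just before the test is named, and the word *dependent* looks deliberate. An arm-against-arm comparison within each group would fit.

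This reading is possible, and it means that the signed-rank test should not be called wrong in every sense. It does not close the gap. No sentence names the arm-against-arm contrast. Handling each task separately argues against execution versus imagery as the pair. In patients with a bionic hand the two arms are recorded at different electrode sites, so that comparison is not like for like. The patient-control comparison would still have no test.

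A second defence is that little depends on this p-value. That stands. The assurance in the Procedure section comes from training with on-screen feedback, the EMG is recorded before scanning, and the small groups follow from a rarity that the plan states openly.

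A reader might infer that the sponsor will link patients to selected controls, so that the result turns on who is picked. The documents propose no such pairing, and any figure for that effect would rest on invented data. A reader might also take the MRI mirroring rule, under which the hemisphere "for the non-dominant hand will, if necessary, be mirrored to be on the left side", to settle which control arm is compared with the affected arm in the EMG analysis. The plan does not extend the rule to EMG.

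**Conclusion.** The concern holds. On the plain reading, the stated test does not fit the stated comparison of unmatched groups of 3, 3 and 10. On the within-person reading, the contrast is missing, patients against controls go untested, and a group of 3 cannot reach two-sided 0.05 (0.25 exact, 0.109 asymptotic). The calculations assume two-sided testing and no ties.

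The severity is minor to moderate. A reader might infer that the fMRI comparison is itself undermined. The documents do not support that: the EMG is a supporting check made in training, and no research question, hypothesis or exclusion rule uses its p-value. Nor does the plan say that it will read non-significance as equal performance; the point is to rule that reading out in advance.

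**What to change.** Amend the EMG paragraph of Design, b) Analysis as follows.

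- For patient-control comparisons, replace the dependent-samples test with the exact two-sided independent-samples Wilcoxon rank-sum (Mann-Whitney) test, using all 10 controls.
- State which patients and which arms are compared, including which control arm is set against the affected arm and which against the healthy arm, and whether the two patient groups are pooled. These are the sponsor's choices, but they should be written down before the data are seen.
- Report the affected arm of patients with a bionic hand descriptively, because its electrode site differs.
- Keep the signed-rank test only for a within-person contrast that is named, and report groups of 3 descriptively there.
- Record which EMG system was used for each person.
- State that the p-values are exploratory, without multiplicity control, and that non-significance is not read as equal performance.

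The cost is a few sentences and one recorded item per person, with no extra participants or measurements. One weakness remains: the plan states no normalisation of the EMG sums, so a between-person comparison stays exposed to differences in recording system and electrode conditions. Recording the system makes this visible but does not remove it.
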